### 9.6.1 Data collection

The data collection period will last six to seven weeks, and will be conducted in parallel in the four countries.

The survey will be conducted by IMS Medical Radar, a division of IMS Health specialising in the conduct of phone and web surveys for more than 20 years. IMS Medical Radar will create a web-based instance survey. The lists of physicians will be loaded into separate databases for the management of the survey. Physicians' answers/data will be collected through a web questionnaire. The survey will collect data in an anonymous way.

As described previously (§9.5.1: Sampling plan and §9.5.2: Study size calculation), physicians will be randomly contacted, mainly by email and also by letters or phone calls when needed, according to their stratum by the IMS Medical Radar team. Their recruitment will be done as follows:

- Physicians will be invited to participate in the survey (via emails/mails or phone calls). The survey background and objectives, the contact information for questions, and the proposed compensation will be explained to the physicians at this step. If they agree to participate in the survey, they will receive a link to access the survey and the instructions for the web questionnaire completion.
- If the questionnaire is not completed and sent to IMS Medical Radar, the physicians will be sent a reminder by email one week after the start of the survey.
- If the target is not achieved in the stratum, a reminder by phone will be conducted 1.5 week after the start of the survey.
- If the questionnaire is still not completed and sent to IMS Medical Radar, the physicians will be sent a last reminder by email two weeks after the start of the survey.

If necessary, i.e. if the minimum number of needed responders is still not reached, the recruitment will be continued by phone to achieve the target in a specific stratum.

A physician will be considered as contacted if he/she has:

- completed the web questionnaire and sent it back to IMS Medical Radar
- refused to participate,
- was tentatively reached out at least 3 times and up to 5 times.

Moreover, a physician will be considered as unreachable if he/she has been contacted between three and five times without any answer.

For each physician of the sample file, the number of contacts, and the date and time when he/she completed the web questionnaire will be recorded. The recruitments in each stratum will be stopped when the target is reached. If the files have been exhausted in any particular stratum, the recruitments in this stratum will be prematurely ended and a strategy will be determined to adjust the sample size with associated weighting.

### 9.6.2 Approaches for increasing the response rate

Physicians are increasingly contacted to participate in web or phone surveys. Their overall response rate of participation remains low according to international studies (8)(9)(10). Holbrook et al. showed that the response rate to surveys continues to decline over time, but a lower rate does not appear to reduce the representativeness of a demographic survey (10). VanGeest et al. conducted a systematic review of 66 published reports on efforts to perform for improving response rates (11). Two general strategies were explored: incentives-based approaches and survey design-based approaches. Financial incentives, even little ones,

were effective in improving physician response rates while non-monetary incentives were much less effective. These measures include the use of a short questionnaire, and questionnaires personalised, and approved by professional associations.

In order to increase the response rate, three actions will be applied to this survey:

- 1) A compensation fee will be proposed to physicians for their participation in the survey.
- 2) All physicians will be sent an email or contacted by experienced operators of IMS Medical Radar with extensive experience in conducting health related surveys.
- 3) Each physician will be emailed or called up to 3-5 times before being considered as “not reachable”, and reminders will be sent by email if IMS Medical Radar does not receive the web questionnaire.

## 9.7 DATA ANALYSIS

### 9.7.1 General statistical consideration

The statistical analysis will be conducted using the SAS® software V9.4 on Windows™ (SAS Institute, North Carolina, USA).

The statistical results of the four countries will be presented in the same report, overall, per country and per physician’s specialty group (Table 9.7.1–1 as an example).

**Table 9.7.1–1: Mock table to implement in the statistical and study reports**

Country	Question 1...				
	General practitioners	Rheumatologists	Orthopedists / orthopedic surgeons	All (unweighted)	All (weighted)
France	(N=xx)	(N=xx)	(N=xx)	(N=xx)	(N=xxx)
answer 1	xx (xx.x%)	xx (xx.x%)	xx (xx.x%)	xx (xx.x%)	xx (xx.x%)
answer 2	xx (xx.x%)	xx (xx.x%)	xx (xx.x%)	xx (xx.x%)	xx (xx.x%)
answer 3	xx (xx.x%)	xx (xx.x%)	xx (xx.x%)	xx (xx.x%)	xx (xx.x%)
Greece	(N=xx)	(N=xx)	(N=xx)	(N=xx)	(N=xx)
answer 1	xx (xx.x%)	xx (xx.x%)	xx (xx.x%)	xx (xx.x%)	xx (xx.x%)
answer 2	xx (xx.x%)	xx (xx.x%)	xx (xx.x%)	xx (xx.x%)	xx (xx.x%)
answer 3	xx (xx.x%)	xx (xx.x%)	xx (xx.x%)	xx (xx.x%)	xx (xx.x%)
Italy	(N=xx)	(N=xx)	(N=xx)	(N=xx)	(N=xx)
answer 1	xx (xx.x%)	xx (xx.x%)	xx (xx.x%)	xx (xx.x%)	xx (xx.x%)
answer 2	xx (xx.x%)	xx (xx.x%)	xx (xx.x%)	xx (xx.x%)	xx (xx.x%)
answer 3	xx (xx.x%)	xx (xx.x%)	xx (xx.x%)	xx (xx.x%)	xx (xx.x%)
Portugal	(N=xx)	(N=xx)	(N=xx)	(N=xx)	(N=xx)
answer 1	xx (xx.x%)	xx (xx.x%)	xx (xx.x%)	xx (xx.x%)	xx (xx.x%)
answer 2	xx (xx.x%)	xx (xx.x%)	xx (xx.x%)	xx (xx.x%)	xx (xx.x%)
answer 3	xx (xx.x%)	xx (xx.x%)	xx (xx.x%)	xx (xx.x%)	xx (xx.x%)
Overall - unweighted results	(N=xx)	(N=xx)	(N=xx)	(N=xx)	(N=xxx)
answer 1	xx (xx.x%)	xx (xx.x%)	xx (xx.x%)	xx (xx.x%)	xx (xx.x%)
answer 2	xx (xx.x%)	xx (xx.x%)	xx (xx.x%)	xx (xx.x%)	xx (xx.x%)
answer 3	xx (xx.x%)	xx (xx.x%)	xx (xx.x%)	xx (xx.x%)	xx (xx.x%)
Overall - weighted results	(N=xx)	(N=xx)	(N=xx)	(N=xx)	(N=xxx)
answer 1	xx (xx.x%)	xx (xx.x%)	xx (xx.x%)	xx (xx.x%)	xx (xx.x%)
answer 2	xx (xx.x%)	xx (xx.x%)	xx (xx.x%)	xx (xx.x%)	xx (xx.x%)
answer 3	xx (xx.x%)	xx (xx.x%)	xx (xx.x%)	xx (xx.x%)	xx (xx.x%)

Note: the table structure may be adjusted in the final study report.

All the analysis will be descriptive in nature and no statistical comparison will be done in this study, as it does not appear to be necessary to answer suitably the survey objectives. Besides as the DHPC and EM were already distributed to all physicians of the selected specialties, a before-after study design with comparison to baseline values is not possible, as well as a case-control study.

Continuous variables will be described by their number (of valid cases, of missing values), mean, standard deviation, and median, Q1, Q3, minimum and maximum.

Categorical variables will be described as the total number and relative percentage per category. These will be the percentage per category.

Free text answers to open-ended questions will be categorised by theme, listed according to the frequency.

Confidence intervals of 95% will be evaluated, when relevant.

The proportions of correct and appropriate answers to selected questions asked in the questionnaire will be expressed among physicians with complete analysable web questionnaires. The endpoint will be assessed overall, by country and among subgroups of physicians' specialty.

In a first step, calculations will be performed on raw data. No projection factor will be applied to generalize the results to the entire prescribers' universe. As a consequence, the line "Overall - unweighted results" will show only the results observed on the overall sample, and will not reflect the countries' universe since this sample is not proportional to the size of IMS OneKey reference files in each country.

In a second step, the results will be weighted according to the real proportion of physicians in each specialty and country in order to accurately reflect the population that the survey seeks to measure.

For each country, the results will be reported according to the prescribers' specialty distributed proportionally to their weight within IMS OneKey reference lists.

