The European Commission (EC) implementing decision was issued on 17 January 2014 (6), and required the distribution of a direct healthcare professional communication (DHPC) (6) to inform prescribers on the updated indication and highlight the genotoxic risk of systemic (oral and intramuscular) thiocolchicoside containing medicinal products.

In addition, further Risk Minimisation Measures were requested: changes to the summary of product characteristics (SmPC) information and patient's information leaflet including information on fertility and potential risk for cancer, adequate educational materials (EM) for patients and prescribers, as further RMMs (7), and a drug utilisation study (DUS) to characterise the prescribing practices during typical clinical use were also requested to evaluate the effectiveness of RMMs.

These measures were included in the MAHs risk management plan (RMP).

Patients being treated with systemic thiocolchicoside should have their treatment reviewed at the next scheduled appointment, and appropriate alternative treatments should be considered.

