## 8. RESEARCH QUESTION AND OBJECTIVES

### 8.1 RESEARCH QUESTION

The research question is whether the DHPC and EM, implemented as RMMs, were effective to ensure:

- correct knowledge of physicians about prescribing conditions and safe use when prescribing systemic thicolchicoside,
- appropriate attitude when prescribing systemic thicolchicoside, in particular as concerns pregnancy, lactation and contraception.

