### 8.2 OBJECTIVE

The survey objective is to measure the effectiveness of the DHPC and EM, implemented as part of RMMs, by ascertaining the proportion of targeted physicians who understood and implemented the latest prescribing conditions and safety information about systemic thicolchicoside provided in the DHPC and EM.

Specific objectives were to evaluate the proportion of physicians who:

- prescribe systemic thicolchicoside only as adjuvant treatment of painful muscle contractures associated with acute spinal pathology in adults and in adolescents from 16 years onwards.
- do not prescribe systemic thicolchicoside for long-term treatment of chronic conditions.
- follow the recommendations regarding the doses and duration restriction:
  - for oral forms: the recommended and maximal dose is 8 mg every 12 hours, i.e. 16 mg per day. The treatment duration is limited to 7 consecutive days.
  - for IM forms: the recommended and maximal dose is 4 mg every 12 hours, i.e. 8 mg per day. The treatment duration is limited to 5 consecutive days.
- do not prescribe systemic thicolchicoside during pregnancy and lactation.
- do not prescribe systemic thicolchicoside in women of childbearing potential not using adequate contraception.

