### 5) Awareness of and attitude towards the latest prescribing conditions and safety information:

- Awareness of the prescribing conditions and safety information about systemic thiocolchicoside presented in the DHPC and EM:

- Awareness of the prescribing conditions and safety information: main concerns perceived
- Sources of knowledge
- Reception of the DHPC by the physician and awareness about the EM
- Physician's intention to consider the prescribing conditions and safety warnings

6) Recent prescriptions details:

The following information related to up to the last five prescriptions to patients will be collected upon physician's recall memory:

- Approximate date of prescription of systemic thiocolchicoside
- Approximate patient' age at the time of prescription (age ranges: <16 or ≥16 years old)
- Gender
- Status at the visit for females of childbearing potential (using or not an effective method of contraception, pregnant or not, planning to be pregnant, breastfeeding)
- Indication for which the drug was prescribed
- Form, number of administrations and dose per administration per day
- Duration of use prescribed
- Concomitant treatment(s) ongoing or written at the time of prescription
- Main reasons for choosing systemic thiocolchicoside
- Information and recommendations provided to the patient when prescribing systemic thiocolchicoside containing medicinal products.

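### Section 9.7.1 rules out any comparison, so an effectiveness question is answered by single-group proportions that cannot be attributed to the DHPC and EM, although receipt is already collected

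*Protocol*

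**What the plan says.** Section 8.1 poses an effectiveness question: "The research question is whether the DHPC and EM, implemented as RMMs, were effective to ensure". Its two targets are what physicians know and how they approach prescribing. Section 8.2 turns it into a measurement: "The survey objective is to measure the effectiveness of the DHPC and EM, implemented as part of RMMs, by ascertaining the proportion of targeted physicians". What is counted is understanding and application of the information.

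Section 9.7.1 makes the whole analysis descriptive and adds that "no statistical comparison will be done in this study, as it does not appear to be necessary to answer suitably the survey objectives". As a further reason it says that before-after and case-control designs are impossible, because the materials went to every physician in the selected specialties. On the breakdown it says "The endpoint will be assessed overall, by country and among subgroups of physicians' specialty". Section 9.7.3 plans, for each relevant question, the proportion with an appropriate answer. The study-objective paragraph of 9.7.1 plans a composite proportion: physicians who got the information, understood it and accept applying it.

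Section 9.3, item 5, lists among the collected variables "Reception of the DHPC by the physician and awareness about the EM", together with sources of knowledge. None of these is named as a grouping variable for the knowledge endpoints.

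Section 7.1 lists a parallel measure required at the same time: "changes to the summary of product characteristics (SmPC) information and patient's information leaflet".

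**The concern.** A proportion in one group describes how much prescribers know. It does not say why they know it. There is no baseline, and the SmPC was rewritten with the same indication, posology, duration limits and contraindications. A physician who never saw the DHPC or EM can therefore still answer correctly, and a high proportion may be reported as success of the materials when receivers and non-receivers answer equally well.

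This is a stated choice and not a gap left for an analysis plan to fill. The protocol asserts that a comparison is unnecessary for its objectives, and an analysis plan that followed it would inherit that position. At stake is the wording of the main conclusion given to the regulator: level of knowledge, or effectiveness of the two measures.

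**Working it through.** **1. The plan's own figure.** Section 9.5.2: n = P(1−P)z²/e² = 0.25 × 1.96² / 0.04² = 600.2, so the stated 600 reproduces. It fixes the precision of one proportion (±4.0 points, unweighted) and carries no information on a difference.

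**2. What a per-question proportion can identify.** Let r be the share of respondents reached, p_R the proportion appropriate among them and p_N that among the rest. The planned quantity is r·p_R + (1−r)·p_N. The protocol gives no value for r; 30%, 50% and 70% are assumptions.

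| Overall | r | No difference | 30-point difference |
|---|---|---|---|
| 50% | 30% | 50 v 50 | 71 v 41 |
| 50% | 50% | 50 v 50 | 65 v 35 |
| 50% | 70% | 50 v 50 | 59 v 29 |
| 75% | 50% | 75 v 75 | 90 v 60 |

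For example, 0.7 × 59 + 0.3 × 29 = 50, and 0.5 × 90 + 0.5 × 60 = 75. Each row gives one overall value under both readings.

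**3. The composite.** Receipt is in its numerator, so it is roughly r × p_R if all who understood accept applying the information (assumption). At r = 50%, no effect gives 0.5 × 75 = 37.5% and a 30-point effect gives 0.5 × 90 = 45%, so it does respond to an effect. But 0.6 × 75 = 45% as well: slightly wider reach with no effect gives the same figure. The composite mixes reach with understanding and is not a contrast.

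**4. The reason for having no comparator.** Section 9.7.1 assumes distribution to all physicians of the selected specialties. Against this:
- Section 9.5.1 says the sampling lists may contain physicians the materials were not aimed at, and section 9.9.5 repeats it as a limitation.
- The French letter in Annex 4 names its addressees, and orthopaedists are not among them. Table 9.5.2–4 plans 50 French orthopaedists.
- Distribution is not receipt, and section 9.3 asks about receipt.

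Unexposed respondents are therefore likely and can be identified. Ruling out before-after and case-control designs does not rule out a cross-sectional contrast inside the sample.

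**5. Precision of that contrast.** Half-width = 1.96 × √[p(1−p) × D × (1/n₁ + 1/n₂)], with n₁ + n₂ = 600.

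D is the design effect from weighting, 600 × Σ W²/n over strata, with counts from Table 9.5.2–2 and allocation from Table 9.5.2–4. French GPs: W = 90,630/163,178 = 0.555, n = 90, W²/n = 0.00343. Italian GPs: W = 45,203/163,178 = 0.277, n = 90, W²/n = 0.00085. All strata with counts sum to 0.00439, so D = 2.64. Letting rheumatologists be 0–5% where their count is unavailable gives 2.53–2.64. Applying the same D to the difference is an assumption.

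| p | Split | D = 1 | D about 2.6 |
|---|---|---|---|
| 75% | 300/300 | 6.9 | 11.2 |
| 75% | 420/180 | 7.6 | 12.2 |
| 50% | 300/300 | 8.0 | 13.0 |
| 50% | 420/180 | 8.7 | 14.2 |

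Figures are percentage points. The 75% rows use D = 2.6 and the 50% rows D = 2.64.

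**The case against.** The protocol is open about being descriptive. Section 8.2 defines effectiveness operationally as a proportion, the ENCePP checklist in Annex 2 says there is no formal hypothesis, and section 7.2 places the survey beside a drug utilisation study. The table layout may change, and an analysis plan that is not shown could add cross-tabulations. All of this stands, but none of it withdraws the sentence calling a comparison unnecessary for the objectives.

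Several stronger readings are tempting, and the documents do not support them:
- A reader might infer that everything rests on one pooled figure that comes out the same whether or not the materials worked. Many proportions are planned, a real effect would raise them, and the composite moves with receipt.
- A reader might infer that poor reach would go unseen. Receipt and awareness are questionnaire variables and would be described like the others, so low receipt would show beside low knowledge. Only the cross-tabulation is unplanned. With receipt tabulated, the levels in receivers and non-receivers might even be backed out by division and subtraction, but only if the composite and the per-question criterion shared a definition.
- A reader might treat the missing success threshold as an error. The protocol contains no threshold rule to test, and whether to set one is debatable and may belong in the analysis plan.

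The most serious objection concerns the remedy. DHPCs went out in February to April 2014 and data collection runs from September to November 2016, so receipt is recalled after about 2.5 years. Better-informed physicians may recall a letter more readily, and section 9.9.3 itself warns of social desirability bias. Revised SmPC text was also annexed to the DHPC, and the package leaflet is a patient document, so SmPC and letter are not cleanly separate sources. These points limit the contrast to a supporting role; they do not make it uninformative.

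**Conclusion.** The point holds in this form: an effectiveness question is answered only by single-group proportions, and any observed proportion of appropriate answers is compatible with an effect of the DHPC and EM or with none. It therefore cannot be attributed to them. The stated reason for having no comparator conflicts with the protocol's own sampling section, its limitations section and the French letter, and would not exclude a contrast by receipt in any case.

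The size shows in the examples: with receipt at 30–70%, a difference of 0 or of 30 points can lie behind the same overall 50%. The missing contrast is estimable at the planned size, to about 7–9 points unweighted and about 11–14 points with weighting. Those figures assume 30–70% receipt, 50–75% appropriate answers overall and a design effect near 2.6 that carries over to the difference. Receipt more lopsided than that would widen them.

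It would be wrong to go further and expect the receipt contrast to settle effectiveness: it rests on self-report and is not randomised.

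**What to change.** In section 9.7.1, replace the sentence that declares a comparison unnecessary. For each endpoint question, report the proportion of appropriate answers among physicians who report DHPC receipt and/or EM awareness, and among those who report neither. Give the difference with a 95% CI, standardised or adjusted for country and specialty. Label it a supportive observational association, subject to recall bias and confounding.

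Describe the overall and subgroup proportions as the level of knowledge among prescribers, not as the effect of the DHPC and EM. Correct the universal-distribution statement so that it agrees with sections 9.5.1 and 9.9.5 and with the addressees of the French letter.

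The cost is a change of wording and one extra set of tables from items already in the questionnaire, with no new data and no additional physicians. The drawback is that the added difference can be over-read, which is why its label should be fixed in the protocol.

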#### Study objective:

The proportion of targeted physicians who received, understood and agreed to implement the latest prescribing conditions and safety information about systemic thiocolchicoside provided in the DHPC and EM will be evaluated. Analysis will be done in total and separately by specialty (GPs, rheumatologists and orthopaedists / orthopaedic surgeons) using proportions and the corresponding 95% Wald confidence intervals.

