**Table 9.5.2–1: Sample size obtained for various precisions and proportions**

Margin of error for 95% CI				
Proportion	5%	4%	3%	2%
10%	139	216	384	864

30%	323	504	896	2,017
50%	384	600	1,067	2,401
70%	323	504	896	2,017
90%	139	216	384	864

Since the proportion of physicians informed about the updated prescribing conditions and recommendations for safe use of systemic thiocolchicoside is not known and there is no evidence supporting the expected proportion, the worst case hypothesis will be assumed considering that 50% of physicians will have received and understood the safety information distributed recently. This assumption yields the largest sample size.

Considering this hypothesis and in order to achieve a CI of 95% with a half-width of 4%, a total of 600 analysable physician questionnaires will be needed for the overall sample. Considering a margin of error of 5% (or 3% respectively) instead of 4%, the required sample size would be 384 (or 1,067) analysable physician questionnaires for the overall sample.

Based on IMS Medical Radar experience from previous similar surveys and estimates and the evaluation of the survey feasibility with four countries, the sample size of 600 is considered for this study. Indeed, the elected sample size should be sufficient to be divided between 4 countries and further between 3 groups of specialities.

It is estimated that about 30% of physicians will not complete the questionnaire until the end or not be analysable (i.e. physicians who respond to questions regarding their knowledge on the updated safety concerns of systemic thiocolchicoside or physicians without any prescription of systemic thiocolchicoside in the last 12 months or physicians who have to interrupt the interview due to an emergency (rare)). Taking into account these respondent physicians without analysable questionnaires, the overall sample size of 780 participating physicians will be required to reach 600 analysable questionnaires (i.e. recruitment of physicians should continue until 600 analysable questionnaires have been reached).

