# number of physicians. %L: percentages per line, %C percentages per column. NA: Not available.

A pragmatic split will be therefore implemented (Table 9.5.2–3) to allocate a sufficient sub-sample size to the less represented countries (Greece and Portugal). To allow this over-sampling of Greece (objective of 120 analysable questionnaires instead of 21 with a proportional allocation) and Portugal (objective of 120 instead of 26, respectively), an under-sampling of the most represented countries France (objective of 180 instead of 353) and Italy (objective of 180 instead of 200) is needed in compensation.

With this sample, it will be necessary to weight the results according to the real proportion of physicians from IMS reference lists or available public information obtained through external sources (e.g. Eurostat or CNOM for France) to allow the representativeness of the overall sample.

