As a consequence, an over-sampling of less frequent specialties will be applied in order to provide a sufficient number of analysable questionnaires (threshold of 30). This allocation is applied to the number of analysable questionnaires. Then, the number of required participating physicians is deducted taking into account 30% of respondents without analysable questionnaires.

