**Table 9.5.2–4: Sample size per country and per specialty**

n (vertical % per country)*	France	Greece	Italy	Portugal	All
Number of physicians with an analysable questionnaire	180	120	180	120	600
GPs	90 (50.0%)	60 (50%)	90 (50.0%)	60 (50%)	300 (50%)
Rheumatologists	40 (22.2%)	30 (25%)	40 (22.2%)	30 (25%)	140 (23.3%)
Orthopedists / orthopaedic surgeons	50 (27.8%)	30 (25%)	50 (27.8%)	30 (25%)	160 (26.7%)
Number of participating physicians required	234	156	234	156	780
GPs	117 (50%)	78 (50%)	117 (50%)	78 (50%)	390 (50%)
Rheumatologists	52 (22.2%)	39 (25%)	52 (22.2%)	39 (25%)	182 (23.3%)
Orthopedists / orthopaedic surgeons	65 (27.8%)	39 (25%)	65 (27.8%)	39 (25%)	208 (26.7%)

\* To be aligned with the n by country, numbers n per specialty have been rounded to the most closed integer.

Since the relative weight of each country and of each specialty in the sampling plan is different from its real relative weight in estimations, the extrapolation of the raw survey results to the overall target population would not be relevant.

A sample adjustment will be performed. The survey results will be weighted to reflect the real proportion of the four countries and within each country to reflect the real proportion of each specialty in order to extend the survey results to the overall target population. Both unweighted (i.e. raw data) and weighted results will be presented in the report.

A weight variable will be applied to each statistical unit (i.e. the analysable physician) during the results calculation in order to correct any over-or under-sampling that may have occurred for a country or specialty. This weight variable will indicate how many unit(s) of the population of interest an observation will count in a statistical procedure. Its value will change per country and per specialty. The weights will be normalised to obtain their sum equal to the sample size.

In order to fill-in each stratum of the sample survey from the IMS OneKey reference files, an independent sample will be selected per stratum through a simple random sampling without replacement.

In each specific stratum, physicians will be contacted according to the order of draw in this stratum. If a physician does not want to participate in the survey, the next one in order of

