### 9.7.3 Questionnaire analysis

The general statistical considerations described above (§9.7.1) will be applied for quantitative and qualitative variables. The number of missing data will be indicated. Missing values are expected to be few and distributed at random. Since there is no applicable method unanimously accepted, there will be no replacement or imputation of missing data (13).

Confidence intervals of 95% will be evaluated for endpoint variables.

Physicians' answers will be analysed by subgroups of physician's specialty per country, and on the overall dataset.

For each question associated to the outcomes included in the main objective, a criterion will be calculated to separate physicians with an appropriate answer (or at least one appropriate response if the corresponding question allows multiple answers or is an open-ended question). These proportions of appropriate answers will be expressed among physicians with complete web-questionnaires.

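### Read naturally, Wald intervals with weights normalised to n = 600 ignore the unequal weights: the weighted total has a half-width of about 6.4%, not the stated 4%

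*Protocol*

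**What the plan says.** - **Interval.** Section 9.7.1 (Study objective) analyses the target proportion in total and by specialty, "using proportions and the corresponding 95% Wald confidence intervals".
- **Weights.** Section 9.5.2, after Table 9.5.2–4, describes the weight in these words: "This weight variable will indicate how many unit(s) of the population of interest an observation will count in a statistical procedure". It continues: "The weights will be normalised to obtain their sum equal to the sample size". Weighted and unweighted results are both to be reported. Sections 9.7.1 and 9.9.5 make the weighted ones the basis for generalising.
- **Precision.** Section 9.5.2 says that "in order to achieve a CI of 95% with a half-width of 4%, a total of 600 analysable physician questionnaires will be needed". The planning assumption is that "50% of physicians will have received and understood the safety information distributed recently". The same section gives margins of 7% for France and Italy (n = 180) and about 9% for Greece and Portugal (n = 120). It warns that subgroups will not have the precision of the whole sample, but gives no such warning for the weighted total.
- **Smaller groups.** Section 9.7.3 adds: "Confidence intervals of 95% will be evaluated for endpoint variables". It analyses answers by specialty within country but names no interval method there. Table 9.5.2–4 plans cells of 30 to 90 physicians.
- **Variance.** No section says how the variance of a weighted proportion is to be computed.

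**The concern.** The allocation is deliberately disproportionate. French GPs are 90 of the 600 planned questionnaires (15%) but more than half of the physicians in Table 9.5.2–2. A weighted total therefore rests largely on one stratum of 90. If the weights are scaled to sum to 600 and then treated as counts in a standard proportion procedure, the software sees 600 equally informative physicians and returns an interval that is too short.

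Section 9.7.1 rules out statistical comparisons, so these intervals are the survey's only statement of uncertainty. The weighted total, the figure meant to describe the target population, is where the protocol promises its best precision. There is a separate question about the Wald form in small cells: when nearly all physicians answer correctly it is too short, and when all do it has zero width.

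**Working it through.** **1. The protocol's own figure.** n = P(1−P)z²/e² with P = 0.5, z = 1.96 and e = 0.04 gives 600.2, so 600 is reproduced. The same formula gives half-widths of 7.3% at n = 180 and 8.9% at n = 120, matching the stated 7% and about 9%. All are simple-random-sampling figures without weights.

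**2. Inputs.** Planned n_h are from Table 9.5.2–4 and population counts N_h from Table 9.5.2–2. Rheumatologists in Greece, Italy and Portugal are marked "NA: Not available". Assumption: they are 0% to 5% of the three specialties there, with 2.5% (the French share) as the central value. Centrally this adds 0.025/0.975 × (5,808; 54,437; 7,014) = 149, 1,396 and 180 physicians, for a total of 163,178 + 1,725 = 164,903.

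**3. Weights.** Normalised weight = (N_h/N) × 600/n_h. Central values: French GPs 3.66, Italian GPs 1.83, Italian orthopaedists 0.67, Portuguese orthopaedists 0.13, Greek rheumatologists 0.02.

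**4. Weighted total.** Let W_h = N_h/N. With equal p across strata, the variance is p(1−p) Σ(W_h²/n_h) and the design effect is 600 × Σ(W_h²/n_h).

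- French GPs: 0.5496²/90 = 0.003356
- Italian GPs: 0.2741²/90 = 0.000835
- Other ten strata together: 0.000113
- Sum 0.004304; design effect 2.58; effective n = 600/2.58 ≈ 232
- Half-width at 50%: 1.96 × 0.5 × √0.004304 = 6.4%
- Coverage of an interval based on n = 600: 2Φ(1.96/√2.58) − 1 = 0.777

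| Assumed share | Design effect | Effective n | Half-width | Coverage with n = 600 |
|---|---|---|---|---|
| 0% | 2.64 | 228 | 6.5% | 77.3% |
| 2.5% | 2.58 | 232 | 6.4% | 77.7% |
| 5% | 2.53 | 237 | 6.4% | 78.2% |

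Simulation of 200,000 surveys gave 77–79%, including cases where p differed between strata. A Wald interval with the stratified variance covered 94.7% at p = 0.5, 93.5% at 0.9 and 92.0% at 0.95.

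**5. Weighted country totals at p = 0.5**, by the same formula within each country. Ranges run over the 0–5% assumption; France needs no assumption.

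| Country | n | Design effect | Half-width | Stated | Coverage if unadjusted |
|---|---|---|---|---|---|
| France | 180 | 1.79 | 9.8% | 7% | 86% |
| Italy | 180 | 1.35–1.48 | 8.5–8.9% | 7% | 89–91% |
| Greece | 120 | 1.24–1.36 | 9.9–10.4% | about 9% | 91–92% |
| Portugal | 120 | 1.39–1.53 | 10.5–11.1% | about 9% | 89–90% |

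**6. Weighted specialty totals.** Unadjusted coverage is about 88% for GPs and 90% for orthopaedists. For rheumatologists it is 71% to 90%; the low end is the 0% assumption, under which only the 40 French physicians carry weight.

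**7. Unweighted cells, exact binomial coverage of Wald limits.**

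| p | n = 30 | n = 40 | n = 50 |
|---|---|---|---|
| 0.50–0.85 | 94–96% | 91–95% | 94% |
| 0.90 | 81% | 91% | 88% |
| 0.95 | 78% | 87% | 92% |
| 0.97 | 60% | 70% | 78% |

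At n = 30, Wilson limits cover 97%, 94% and 94% at p = 0.90, 0.95 and 0.97. The chance that all 30 are correct, giving a zero-width Wald interval, is 0.95³⁰ = 21% at p = 0.95 and 0.97³⁰ = 40% at p = 0.97.

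**The case against.** The strongest reply is that the protocol never writes √(p(1−p)/600). A Wald interval is the estimate plus or minus 1.96 standard errors and leaves the standard error open. Scaling weights to sum to n does not change a stratified variance, and the estimator could sit in a statistical analysis plan that is not shown. This stands in part. A reader might infer that the weighted intervals are certain to be wrong, or that the Wald form itself is to blame for the weighted problem. The documents support neither: the fault depends on how the variance is computed, and Wald limits with a stratified variance are sound for the total. The reply does not rescue the stated 4% and 7%, which the weighted estimates do not deliver under any correct variance.

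A reader might also infer that cells of 30–50 physicians fail generally, or that all the intervals cover only 60–80%. They do not. The Wald sentence covers only the total (n = 600) and the three specialties (n = 300, 140 and 160); use in the smaller cells is an extension through Section 9.7.3. Even there, coverage is adequate at the planning value of 50% and up to 85%. The protocol gives no basis for expecting 97%.

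Nor would the intervals show ±4% whatever the data: at n = 600 and p = 0.9, the unadjusted half-width is 2.4%.

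Finally, the missing rheumatologist counts affect 100 planned physicians. Leaving those physicians out altogether (n = 500) gives a design effect of 2.20 and coverage of about 81%, but the half-width is still 6.5%. The survey is descriptive and has no success threshold, and point estimates are unaffected.

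**Conclusion.** The point holds in a conditional form for the intervals and outright for the planned precision. Under the Table 9.5.2–4 allocation and the Table 9.5.2–2 counts, the weighted total has a half-width of about 6.4% at 50%, not 4%, and weighted France about 9.8%, not 7%. If the weights are handled as the text most naturally reads, the interval for the weighted total covers about 77–78%, for France about 86%, and for the other countries about 89–92%.

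These figures assume that the planned cell sizes are met, that p is equal across strata for the formula, that rheumatologists are 0–5% where not counted, and that the physician lists eventually used for weighting resemble Table 9.5.2–2. The small-cell problem is real but narrow: about 60–81% coverage at n = 30 for proportions of 0.90–0.97, and only if Wald limits are carried into those cells.

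**What to change.** 1. **Section 9.7.1:** state that all weighted proportions will have a design-based variance using the 12 strata and the sampling weights. Wald limits may stay for the weighted total.
2. **Section 9.5.2:** restate the expected weighted precision at 50% as about ±6.4% overall and about ±9.8% for France, with the rheumatologist assumption given. Keep ±4% and ±7% for unweighted results only.
3. **Sections 9.7.1 and 9.7.3:** use Wilson or exact limits for unweighted proportions in small cells.

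The cost is a few sentences and a survey-analysis procedure in the SAS software already named. No new data are needed, but the reported intervals become wider. Holding ±4% for the weighted total under this allocation would instead need about 1,550 analysable questionnaires (600.2 × 2.58; range about 1,520 to 1,580), so restating the precision is the practical course.
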